## NUMBER OF SUBJECTS TO BE ENROLLED

Based on the results of a recently concluded CPAP intervention study for chronic cough, mean change in LCQ with CPAP was + 4.1 (with 4.14 SD in baseline and followup LCQ scores)

Mean change in LCO with placebo was 1.1 (Lancet 2012)

Expected difference between mean LCOs of two groups 3.0

- To achieve 80% difference to detect a significant difference of 0.05 level for a difference means of 2.58, 19 subjects per group needed assuming no attrition using a mixed models analysis of repeated measures data.

- Assuming 33% attrition rate due to CPAP noncompliance, 29 subjects per group needed.

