## STUDY PROCEDURES

### 1. CONSENT FORM 2. STUDY QUESTIONNAIRES

- Leicester-cough questionnaire (LCQ) at baseline, 6 weeks, 12 weeks
- Cough VAS scale at baseline, 6 weeks and at 12 weeks
- GERD-QoL questionnaire (GERD-QoL) at baseline and at 6 weeks
- Sino-nasal outcome test (SNOT-20) at baseline and at 6 weeks
- Asthma life questionnaire at baseline and at 6 weeks
- Laryngeal dysfunction scores (LDQ) at baseline and at 6 weeks

3. Cough monitoring for 24 hours, at baseline and at 6 weeks and 12 weeks.
4. CPAP data download at 6 weeks, 12 weeks
5. Exhaled breath condensate at baseline, 6 weeks and 12 weeks.

Once patients are enrolled, they will be randomized to either straight CPAP or sham CPAP. Randomization will be done by study coordinator, [name] and treating physicians (and investigators) will be blinded to whether the patient received straight CPAP or sham CPAP. Patients will be evaluated at 6 and 12 weeks after randomization as part of study. At 6 weeks, patients will be unblinded and placed back on straight CPAP. The pressure on straight CPAP will be determined according to the results of the polysomnography or they will be kept on 10cm of CPAP (adjustments to this may be made by the study coordinator, [name] who is the CPAP coordinator for the Sleep Center). For sham CPAP, patients will be kept at 1-2cm of pressure as per sham CPAP recommendations and no adjustments to this will be made although there may be adjustments made in mask or interface used for the CPAP.

---

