### PRIMARY END-POINT

1. Change in LCQ score in CPAP-treated patients vs. sham CPAP-treated patients. This will be compared between baseline LCQ score prior to initiation of CPAP or sham CPAP and compared to the LCQ score at 6 weeks.
2. Change in Leicester cough monitoring measured at baseline and at 6 weeks after CPAP or sham-CPAP therapy.
3. Change in measurements of exhaled breath condensate 8 isoprostane, IL-6, nitrite/nitrate, H2O2 and LTB4 at baseline and at 6 weeks.

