## PATIENTS ON STRAIGHT CPAP FOR 6 WEEKS

## VISIT 3 (+12 wk) ADMINISTRATION OF LCQ, SMART-CARD DATA DOWNLOAD, EBC

## STATISTICAL ANALYSES

Each patient will serve as his or her control in terms of 6 weeks assessment of LCQ change following sham CPAP or straight CPAP therapy. Similar analyses are expected for GERD-QoL scores, Cough monitoring and EBC assessments.

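### The LCQ analysis is described as unadjusted change from baseline; adjusting 6-week LCQ for baseline would be more precise with the same data, and the power statement lacks the inputs needed to check 19 per group.

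*Combined protocol and SAP*

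**What the plan says.** Under PRIMARY END-POINT, the first item is "Change in LCQ score in CPAP-treated patients vs. sham CPAP-treated patients", measured from baseline to 6 weeks. Under STATISTICAL ANALYSES, the only description of the method is "Each patient will serve as his or her control in terms of 6 weeks assessment of LCQ change". No test, between-arm model or baseline covariate is named.

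Under NUMBER OF SUBJECTS TO BE ENROLLED, the inputs are a mean LCQ change of 4.1 with CPAP ("with 4.14 SD in baseline and followup LCQ scores") and 1.1 with placebo, so "Expected difference between mean LCOs of two groups 3.0". The power sentence then switches to another target: "for a difference means of 2.58, 19 subjects per group needed assuming no attrition using a mixed models analysis of repeated measures data". The last step is "Assuming 33% attrition rate due to CPAP noncompliance, 29 subjects per group needed", which matches the 58 subjects under Sample Size.

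LCQ is collected at baseline and 6 weeks, and again later ("VISIT 3 (+12 wk) ADMINISTRATION OF LCQ"). By that later visit both arms are on active treatment: "At 6 weeks, patients will be unblinded and placed back on straight CPAP".

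**The concern.** Two things stand out. First, the described analysis subtracts baseline from the 6-week score and stops there. In a randomised two-arm comparison with equal SDs at the two visits, subtraction over-corrects for baseline whenever the correlation is below 1. Regressing the 6-week score on baseline and arm uses the same two measurements better. A trial of 58 patients has little precision to spare.

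Second, the reader cannot tell what 19 per group rests on. The SD given is that of the scores, while the quantity analysed is change. Moving from one to the other needs the within-patient correlation, which is not stated. Nor are the sidedness, the mixed-model contrast, or the reason for 2.58 in place of 3.0. Whether 19 evaluable patients per group cover the plan's own expected difference of 3.0 depends on that missing correlation and on the analysis chosen.

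**Working it through.** **Inputs from the document.** LCQ SD 4.14 at baseline and follow-up; differences 2.58 and 3.0; level 0.05; 19 per group before attrition and 29 after.

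**Assumptions.** Two-sided test. The correlation ρ between baseline and 6-week LCQ is not in the document, so it is shown at 0.5, 0.6 and 0.7 and at the value that would reproduce 80%. Powers use the noncentral t distribution unless stated.

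**Sums that reproduce.** 4.1 − 1.1 = 3.0. 19/(1 − 0.33) = 28.4, so 29 per group. 2 × 29 = 58.

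**The plan's 19 per group.**

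- Using 4.14 directly as the SD of the quantity compared: 2.58/(4.14 × √(2/19)) = 2.58/1.343 = 1.92, which gives 46% power; 80% would need 42 per group. One-sided, by the normal approximation, power is 61% and 32 per group are needed.
- A one-sample (paired) formula with SD 4.14, two-sided and by the normal approximation, gives 21, with 77.5% power at 19. It contains no sham comparison.
- Two-arm change score: SD of change = 4.14 × √(2(1 − ρ)). For 80% at 19 per group and 2.58, this SD must be about 2.76, so ρ = 1 − 2.76²/(2 × 4.14²) = 0.78. For 3.0 it must be about 3.21, so ρ = 0.70.
- Mean of three visits, normal approximation: n = 2 × (1.96 + 0.842)² × 4.14² × (1 + 2ρ)/3 ÷ 2.58² = 18.9 at ρ = 0.2. This also reaches 19, but it averages in baseline and the 12-week visit, when everyone is on CPAP, so it does not match the 6-week end-point.

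So 19 is attainable, but each route that gives 19 with 80% power needs a value that the document does not state.

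**Change against baseline-adjusted.** The adjusted residual SD is 4.14 × √(1 − ρ²). The variance ratio, adjusted to change, is (1 − ρ²)/(2(1 − ρ)) = (1 + ρ)/2, that is 0.75, 0.80 and 0.85 at ρ = 0.5, 0.6 and 0.7. It is below 1 for every ρ below 1. Chance baseline imbalance inflates the adjusted variance by 1 + 1/(2n − 4), which is 35/34 at n = 19. With that included, the ratio stays below 1 up to ρ = 68/35 − 1 = 0.94. Degrees of freedom are 2n − 2 (change) and 2n − 3 (adjusted).

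Example at ρ = 0.6, difference 3.0, 19 per group:

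- Change: SD 3.70, standard error 3.70 × √(2/19) = 1.20, 3.0/1.20 = 2.50, power 68%.
- Adjusted: SD 3.31 × √(35/34) = 3.36, standard error 1.09, 3.0/1.09 = 2.75, power 76%.

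Power, change → adjusted (allowing for chance imbalance):

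| ρ (assumed) | 2.58, n = 19 | 3.0, n = 19 | 3.0, n = 29 |
|---|---|---|---|
| 0.5 | 46 → 57% | 58 → 70% | 77 → 87% |
| 0.6 | 55 → 63% | 68 → 76% | 86 → 92% |
| 0.7 | 67 → 73% | 80 → 85% | 94 → 96% |
| 0.78 | 80 → 83% | 90 → 92% | not tabulated |

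The last row uses the unrounded ρ of 0.777. Patients per group for 80% power at 3.0, at ρ = 0.5, 0.6 and 0.7, are 31, 25 and 19 (change) and 24, 21 and 17 (adjusted).

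**The case against.** **No sum is shown to be false.** This stands. A reader might infer that 19 per group is an arithmetic error, or that the trial is underpowered. The document supports neither. A correlation near 0.78 gives exactly the stated power, the target of 2.58 is stricter than the derived 3.0, and the remaining sums are right. What can be said is that 19 cannot be verified.

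**The mixed model may already be the efficient analysis.** A reader might also infer that the plan has committed to an unadjusted change score. It has not done so in terms. A mixed model with baseline means held equal between arms would capture most of the gain. A group-by-time test with baseline as a free outcome is equivalent to the change analysis. The document does not say which is meant, and the one sentence on analysis points to change. The objection limits the claim to what the text describes; it does not remove the need to name the model.

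**The gain is small where the plan's claim is true.** Also correct: at the correlation that makes 19 right for a change analysis, adjusting adds about 3 points for 2.58 and about 2 for 3.0. The gain reaches 5 to 11 points only at correlations of 0.7 down to 0.5.

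**The plan enrols 29 per group, and its attrition is CPAP non-compliance.** Non-adherent patients may still complete an LCQ, and power is then better than at 19. The n = 29 column is an upper bound, before any dilution of the effect by non-adherence.

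**Conclusion.** The point holds as one of analysis efficiency with unspecified power inputs. As described, the LCQ analysis makes no adjustment for baseline. With equal SDs, an adjusted 6-week comparison is more precise: at 19 per group, about 11, 8 and 5 points more power for 3.0 at correlations of 0.5, 0.6 and 0.7, and 2 to 3 points near 0.78. The correlation needed for 80% power at 3.0 with 19 per group is about 0.70 for the change analysis.

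The direction of the gain rests on the plan's own equal SDs. Its size rests on the assumed correlations and on a two-sided test, neither of which the document gives.

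**What to change.** Under STATISTICAL ANALYSES, for LCQ, replace the own-control sentence with:

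> The primary LCQ analysis compares 6-week LCQ between CPAP and sham CPAP, adjusted for baseline LCQ (ANCOVA), two-sided 0.05, reported as the adjusted difference with its 95% confidence interval.

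A mixed model of baseline and 6-week LCQ with baseline means held equal between arms would serve equally well, if stated in those terms.

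As a supporting change, under NUMBER OF SUBJECTS TO BE ENROLLED restate the power for that analysis with a single target difference (3.0 as derived, or 2.58 with the reason) and a sourced correlation. If the source study does not supply a correlation, print the range: for 3.0 at 19 per group, 70, 76 and 85% at assumed correlations of 0.5, 0.6 and 0.7.

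The cost is one reworded sentence and one recalculated paragraph. Baseline and 6-week LCQ are already collected, so there are no new data, visits or patients, and enrolment stays at 58. Adjustment uses one degree of freedom, which the figures include. The one drawback is that the restated power at 19 per group may fall below 80% if the correlation is low.
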